## **Food cues activate brain reward systems that prompt cravings and eating.**

Though complex neural regulatory systems monitor the body's energy stores and prompt feeding behaviors to match energy requirements (22), non-homeostatic (hedonic) mechanisms also drive consumption of highly palatable foods (23,24). The dopaminergic mesolimbic pathway is central to hedonic eating because it detects rewarding food stimuli and prompts cravings and eating (25). In addition to the sight and smell of actual food, neuroimaging studies from our group (1,25) and others (26,27) demonstrate that images of food also stimulate this pathway and that food-cue-related activity in this pathway is related to subsequent snack food consumption (28) and weight gain (25). Limiting non-homeostatic cued eating is essential for healthy weight maintenance, because even modest caloric excesses can accumulate into substantial weight gain over time (29,30).

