**Participant recruitment and enrollment.** We will recruit 150 children, aged 13-17-years-old using listservs, community postings and in-person recruitment in family-centered organizations such as schools, pediatric clinics, and community centers, and postings on social media platforms such as Facebook. Participants may be recruited under study-specific recruitment efforts and/or our general recruitment efforts for all the studies our lab is currently running. In addition, we will also recontact participants from a list of participants who have previously enrolled in studies in our lab. Parents of these children have consented to being contacted for future studies. We will periodically send all families in our database e-cards to thank them for their participation in our studies and also to let them know that we are recruiting participants for multiple studies. The study will be promoted as a study to investigate how children process information from different types of media; specific study goals will be concealed from children until the end of the study to prevent biasing participant behavior. However, parents of children will be told the true nature of the study prior to providing consent for their child's participation so that they can make an informed decision. We will ask the parent not to share the true purpose of the experiment until the study is over. Exclusion criteria will include inadequate English proficiency, a vision disorder that is not corrected with corrective lenses, and relevant food allergies. Exclusion criteria will be confirmed by the parent during the initial consent procedure via telephone. After initial parental consent is obtained verbally via telephone, study staff will schedule three dinnertime or lunchtime appointments and ask that children eat normal meals and snacks the day of the appointment, but refrain from eating within 45 minutes of their appointment. At the appointment, staff will obtain informed consent/assent. Following consent, children will complete the experimental flow in Figure 2.

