**Eating in the absence of hunger (EAH) measurement.** When the child finishes the memory game, he/she will be asked to "wait in the room" for 10 minutes while the experimenter allegedly takes care of tasks in a different room. During this period, the waiting room will contain pre-weighed snack items and games to measure EAH using established methods (1,58). The pre- and post-weights of each snack item will be used to calculate the number of kCal the child consumed. The EAH phase will take place within 20 minutes of the standardized dinner.

**Assessing usual media multi-tasking.** Children will complete the media multi-tasking index (MMI) (8). This index asks about media multitasking with other print and digital media during four primary activities: 1) watching TV or movies, 2) playing video games, 3) reading books or magazines (not assigned for school), and 4) doing homework. For each activity, participants reported the frequency with which they multitasked by engaging in the other activities by using a 5-point likert scale (i.e., 0=Never, 1=Rarely, 2=Sometimes, 3=Often, 4=Always). A usual media multitasking score was computed by taking the average of the Likert response. The score ranges from 0 to 4 with a higher score indicative of higher self-reported usual media multitasking, on cognitive control tasks (8,59,60).

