## 8. Deception

Does any part of this study involve deception or withholding of information from participants?

Yes       No

If Yes, provide an explanation which addresses the following:

- A description of the deception being used
- Why the deception is necessary
- A plan for debriefing, or providing subjects with the pertinent information after participation

We will not completely disclose the purpose of the main study or the purpose of the sub-study to participants in order to avoid bias. This may lead to the participants feeling distressed about being deceived or distrustful of scientific research. In order to address the risks associated with not completely disclosing the research aims of the study, we will send a letter to parents that explains the full purpose of the study when the study is complete. We will explain that we did not reveal the study purpose because we thought that such knowledge might have influenced their children's behavior. We will provide our contact information so that parents and/or their children can discuss the study further if they desire. These procedures will also be followed for the sub-study.

The full debriefing of the main study reveals the objective of the Tetris game, which is to assess how much attention participants pay to the peripheral food cues as they play Tetris. However, because the Tetris game is used for the same purpose in the sub-study, fully debriefing participants after they finish the main study but before they complete the sub-study (as is our current protocol) may affect their responses in the Tetris game during the sub-study. For this reason, those participants in the main study that choose to participate in the sub-study will be debriefed of both studies after they complete the sub-study.

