## 10. Recruitment

**Describe method(s) of recruitment. Associated advertisements and other materials to be used for recruitment should be uploaded to the ‘Consent Forms and Recruitment Materials’ page in Rapport.**

We will recruit 150 children, aged 13-17-years-old using listservs, community postings and in-person recruitment in family-centered organizations such as schools, pediatric clinics, and community centers, and postings on social media platforms such as Facebook. In addition, we will also recontact participants from a list of participants who have previously enrolled in studies in our lab. Parents of these children have consented to being contacted for future studies. We will periodically send all families in our database e-cards to thank them for their participation in our studies and also to let them know that we are recruiting participants for multiple studies. We will target our recruitment to communities of lower to middle socioeconomic status by recruiting from communities with higher rates of eligibility for free/reduced meals in the National School Lunch Program within the town’s public elementary schools; those data are publicly available via state-level departments of education. By expanding our recruitment catchment area and adding additional staff time to recruitment, we are confident that we can reach our enrollment target within the study period. Participants for the sub-study will be recruited from the group of participants who successfully complete the main study and who express interest.

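### Children from the lab's earlier studies are recontacted without screening for, or recording, earlier exposure to or debriefing about food-cue or snack-intake tasks

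*Combined protocol and SAP*

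**What the plan says.** **Source of participants.** Section 3 (Participant recruitment and enrollment) and section 10 (Recruitment) both list former participants as a source: "we will also recontact participants from a list of participants who have previously enrolled in studies in our lab". The only condition attached is parental permission: "Parents of these children have consented to being contacted for future studies".

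**Eligibility.** "Exclusion criteria will include inadequate English proficiency, a vision disorder that is not corrected with corrective lenses, and relevant food allergies". Earlier participation, earlier exposure to the tasks and earlier debriefing are not mentioned.

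**Concealment.** Section 3 says that "specific study goals will be concealed from children until the end of the study to prevent biasing participant behavior". Section 11 repeats this. Parents learn the true purpose before consent, and section 3 asks them to keep it from the child while the study runs.

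**Debriefing.** Section 8 plans a letter to parents once the study is complete. It says that "The full debriefing of the main study reveals the objective of the Tetris game" and that "fully debriefing participants after they finish the main study but before they complete the sub-study (as is our current protocol) may affect their responses"; the sentence goes on to limit this to the Tetris game in the sub-study. For that reason, children who join the sub-study are debriefed only after finishing it.

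**Covariates and analysis.** Neither the list of potential covariates nor section 4 (Analysis) includes prior lab participation.

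**The concern.** The eye-tracking outcomes and EAH are behaviors that a child can control once he or she knows what is being measured. The unattended snack period also rests on a cover story. The plan protects naivety inside the study, but does not check whether a child arrives with it.

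Some overlap in tasks is plausible. The EAH method is cited to references 1 and 58, and the Introduction attributes reference 1 to the same group. The preload-meal method is cited to reference 48, a study of food advertising and excess consumption in children that shares authors with reference 1.

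A child who knows that snacks are weighed, or that the side pictures matter, might restrain eating or gaze in all three conditions and so respond less to the condition itself. If so, the contrasts of multi-task versus control and sustained attention versus control would shrink, and a null result would be harder to interpret. Because prior participation is not recorded, the analysis could not examine this afterwards.

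**Working it through.** **1. The passages side by side**

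| Question | What the documents show |
|---|---|
| Are former lab participants recruited? | Yes (sections 3 and 10) |
| Is prior exposure or debriefing an exclusion? | No; the listed exclusions are English proficiency, vision and food allergy |
| Is it recorded, adjusted for or examined in a sensitivity analysis? | No (Potential covariates; section 4) |
| Does the plan accept that knowing a task's aim can change behavior? | Yes, for Tetris in the sub-study (section 8) |
| Which earlier studies, with which tasks, and was the child debriefed? | Not stated |
| How many children come from the list? | Not stated |

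The omission is therefore documented. Its consequence is not.

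**2. The plan's own power figure**

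Section 4 gives n = 107, two-tailed alpha 0.05 and 80% power for |r| = 0.27. By Fisher's z, power = Φ(atanh(r)·√(n − 3) − 1.96). Here atanh(0.27) = 0.2769 and √104 = 10.198, with product 2.823. Power = Φ(0.863) = 0.806, so the stated 80% reproduces. This figure is context only; the point does not dispute it.

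**3. What dilution would do (assumed inputs)**

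Let a share p of children be non-naive and their condition effect be reduced by a fraction k. The average effect is then multiplied by 1 − pk and the effective sample size by (1 − pk)². This ignores any change in outcome variance. The documents give neither p nor k. The last two columns apply the shrinkage to the plan's r = 0.27 at n = 107, and compare it with leaving the non-naive children out at the full r = 0.27.

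| p | k | 1 − pk | (1 − pk)² | Power, all 107 kept | Power, non-naive left out |
|---|---|---|---|---|---|
| 0 | – | 1 | 1 | 0.81 | – |
| 10% | 0.5 | 0.95 | 0.90 | 0.76 | 0.76 (n = 96) |
| 20% | 0.5 | 0.90 | 0.81 | 0.72 | 0.71 (n = 86) |
| 30% | 0.5 | 0.85 | 0.72 | 0.66 | 0.65 (n = 75) |
| 10% | 1 | 0.90 | 0.81 | 0.72 | 0.76 (n = 96) |
| 20% | 1 | 0.80 | 0.64 | 0.61 | 0.71 (n = 86) |
| 30% | 1 | 0.70 | 0.49 | 0.50 | 0.65 (n = 75) |

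With k = 0 nothing is lost. The plan's r concerns correlations with EAH, not the condition contrasts, so the powers show proportion only.

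**4. What the table implies for the remedy**

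Keeping non-naive children is the better choice for power when (1 − pk)² > 1 − p. At k = 0.5 the left side is 1 − p + p²/4, so keeping them is marginally better for any p. At k = 1 it is (1 − p)², and leaving them out is better. Since k is unknown, dropping every former participant from the primary analysis is not justified. Recording status and running a sensitivity analysis is.

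**The case against.** The strongest case against has five parts.

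- **Scope of section 8.** A reader might infer that debriefing main-study finishers contaminates the main study. The documents do not support that. The warning concerns finishers who go on to the sub-study, and section 10 draws sub-study children only from main-study completers, so debriefing cannot alter a child's own main-study data. The practice described as current is the one section 8 then changes for sub-study joiners.
- **Protections in place.** A reader might also infer that the main study is unprotected. It is not: goals are concealed, parents are asked to keep them confidential, and the letter goes out when the study is complete. What remains is that these steps cannot undo what a child learned in an earlier study.
- **Prior exposure is inferred.** Nothing says that the earlier studies used Tetris or EAH, or that their children were debriefed. Section 8's concession covers Tetris, so extending it to EAH is a further inference. Spread of information between children at shared schools or community centers has no basis in the documents. All this stands, and it is why the size is left open.
- **Familiarity is universal by visit 2.** Every child does Tetris and the snack wait at all three visits, so having done the tasks before adds little. This largely stands; earlier debriefing is the more serious possibility.
- **Within-child contrasts.** A stable shift across the three conditions cancels. This stands. Only a weaker response to condition would survive in the contrasts, and that is possible but not established.

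**Conclusion.** The point holds in limited form. The plan recruits former lab participants and relies on concealment, but neither screens for nor records earlier exposure to, or debriefing about, food-cue or EAH tasks. Its own reasoning for the sub-study shows that it regards such knowledge as able to change Tetris responses.

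The direction of any harm is most likely dilution of the condition contrasts. The documents give no ground for expecting a false positive. The size is unknown. A 5% to 15% smaller effect, or a 10% to 28% loss of effective sample, follows only from assuming 10% to 30% non-naive children with a halved effect, and should not be read as an estimate. The change is worth making because it is cheap and because without the record the question cannot be answered later.

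**What to change.** 1. **Recontact.** When drawing on the lab's list, leave out children already debriefed about a food-cue or EAH task. Other former participants stay eligible.
2. **Record and test.** For every child, record prior lab participation, the tasks done and whether the child was debriefed. Prespecify in section 4 a sensitivity analysis of both primary contrasts, for each primary outcome, without previously exposed or debriefed children. Keep them in the primary analysis.

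**Cost.** A filter on the lab's own contact list, a screening question, a slightly smaller recontact pool and one extra analysis. That analysis will have less power than the main one, so it should be read for consistency of the estimates, not for significance.

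**Clarification only.** State whether the end of the study, for concealment and for the debriefing letter, means the child's last visit or the last child's last visit. Delaying all letters further would be a disclosure trade-off for the ethics committee, and on one reading it is already the plan, so no change is asked for here.

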## APPROACH

### Main Study

We will achieve our aims by having 13-17-year-olds visit the laboratory on three occasions to complete each of three tasks: a media multi-tasking paradigm, an eye-tracking task that measures attention to food cues, and an EAH paradigm. Additionally, children will complete a questionnaire-based media multi-tasking scale. Children will be randomized to complete the multi-task, sustained attention, or control condition of the media multi-tasking paradigm during their first visit and will complete the alternate conditions during their second and third visits. The experimental flow for individual laboratory visits is shown in Figure 2.

**Preload meal.** In order to control for satiety, children will be fed a standardized palatable dinner at the beginning of the study using established methods (48).

**Multi-tasking experimental manipulation.** Immediately following dinner, children will complete one of three conditions (attentional training, acute media multitask, or control) in a modified version of the Go/No-go task to simulate media-multitasking.

**Attentional training.** A Go/No-go task was used to train sustained attention. For the task, a blue or yellow dot briefly appeared for between 20 - 1500 msec and then disappeared. Participants were instructed to respond to the blue dot by pressing the space bar as quickly as possible (Go trials) and were told not to respond when presented with a yellow dot (No-go trials). At random intervals between 2000 – 5000 msec the messaging bot would ding and send participants a text message. The text message included questions about random facts; for example, how many teeth does an alligator have? Participants were instructed to ignore the messages and focus on the Go/No-go task. By asking participants to practice ignoring incoming messages and focus on a task designed to increase sustained attention, the training condition was designed to reduce acute media multitasking and increase sustained attention. Participants completed 100 Go trials and 100 No-go trials randomized on a trial-to-trial basis. There was a total of 60 messages sent to participants.

**Acute media multitask.** Participants were asked to monitor and engage with two different tasks simultaneously. On the left side of the screen, a blue dot would briefly appear and then disappear (between 20 - 1500 msec) and participants were instructed to press the space bar as quickly as possible whenever the blue dot appeared. On the right side of the screen, a messaging bot would ding and send participants a text message randomly every 2000 – 5000 msec. The questions were identical to those from the attentional training task.

Unlike the attention training condition, participants were asked to attend to and type answers to the text messages as possible. Participants were instructed to guess if they did not know the answer. Participants completed 100 trials and received a total of 60 messages.

**Control condition.** For the control condition, participants were asked to passively watch a video simulation of the media multitask condition with no specific instructions of where to look.

**Attention to peripheral cues.** Immediately following the multi-tasking experimental manipulation, children will play a game of Tetris that measures attention to peripheral cues using eye-tracking. On either side of the game screen are pictures of food and animals that change periodically. Study staff will set up children with the task, provide directions, have children do a practice trial game, and clarify directions if necessary. The food cue is chosen at random on a game-to-game basis. To encourage gameplay concentration, children are encouraged to complete as many games as possible within 10 minutes. This game has high ecological validity because it mimics Internet advergames that are used to advertise products to children (2). We will use established eye-tracking metrics to measure attention to food cues. The amount of attention given to peripheral cues while playing the video game Tetris will be calculated for each participant after they completed each experimental condition. Areas of interest will be created around distractor images, defined as the area of the image, 250 X 250 pixels. First fixation duration will be measured as the average amount of time an adolescent spent fixating a distractor the first time that they looked at it. Cumulative fixation duration will be calculated as the total amount of time participants spent fixating distractors, summed over all fixations. For both measures, a fixation duration will be defined as any stationary period lasting at least 100 milliseconds. Eye-tracking will be recorded using the EyeLink 1000 Plus (SR Research, Ottawa, Ontario, Canada). The EyeLink is a robust desktop configuration that also includes facial recognition software to monitor head movements. This ability to compensate for head movements is particularly useful because it assures that when participants look away from the stimulus and then return to it, the system will automatically reacquire the eye. Critically, the video used to track the eyes is not saved and the person's likeness is never recorded.

**Eating in the absence of hunger (EAH) measurement.** When the child finishes the memory game, he/she will be asked to "wait in the room" for 10 minutes while the experimenter allegedly takes care of tasks in a different room. During this period, the waiting room will contain pre-weighed snack items and games to measure EAH using established methods (1,58). The pre- and post-weights of each snack item will be used to calculate the number of kCal the child consumed. The EAH phase will take place within 20 minutes of the standardized dinner.

**Assessing usual media multi-tasking.** Children will complete the media multi-tasking index (MMI) (8). This index asks about media multitasking with other print and digital media during four primary activities: 1) watching TV or movies, 2) playing video games, 3) reading books or magazines (not assigned for school), and 4) doing homework. For each activity, participants reported the frequency with which they multitasked by engaging in the other activities by using a 5-point likert scale (i.e., 0=Never, 1=Rarely, 2=Sometimes, 3=Often, 4=Always). A usual media multitasking score was computed by taking the average of the Likert response. The score ranges from 0 to 4 with a higher score indicative of higher self-reported usual media multitasking, on cognitive control tasks (8,59,60).

**Potential covariates.** We will assess potential covariates for potential inclusion in analyses for Aims 1-3. Given the association between exercise and increased attentional processing in preadolescent children (61), we will assess usual **physical activity** using the ActiGraph GT3X-BT triaxial accelerometer (ActiGraph LLC, Pensacola, FL) for 7 days between the first and second visit using established methods (62-64). Relatedly, it is important to record physical activity to isolate the effect of media multi-tasking on cued eating, from the effect of general sedentary behavior that media multi-tasking is potentially a proxy. Children will also be asked to self-assess their **pubertal maturation** using the Pubertal Development Scale, which has shown strong validity and acceptability in our age group (65-67). Before administering this scale, the experimenter will emphasize that responses are voluntary, and that if the child simply does not understand some questions, his/her parent will offer responses. We will have children report on their **media exposure** using a questionnaire adapted from the Kaiser Foundation (14), and their **health knowledge and attitudes about the provided food** (68). Parents will report on their child's **sleep duration** using the Adolescent Sleepiness Scale, the Adolescent Sleep-Wake Scale, and the Adolescent Sleep Hygiene Scale (69), eating behaviors using the child eating behavior

questionnaire (CEBQ) (71), and **sociodemographic variables** (i.e., education, household income, race, and ethnicity). **Height and weight** will be measured using standard methods (72) to calculate age- and sex-specific **BMI z-scores** (73). These variables will be collected via a parent questionnaire that will be completed by the parents via an online questionnaire sent securely through RedCap.

